15.1.7. Determination of Patients/Data for Analysis

A modified intention-to-treat protocol will be utilized for the primary efficacy analysis: all subjects for whom either AAD or cryoballoon ablation therapy is initiated will be analyzed according to their randomization status. Subjects who withdraw consent between randomization and initiation of therapy will be excluded from the primary efficacy analysis.

15.2. Primary Safety Objective

Demonstrate an acceptable safety profile of the cryoballoon ablation procedure as a first line therapy in a non-drug refractory paroxysmal AF population.

15.2.1. Hypothesis

The following hypothesis will be tested in a one-sided test with $\alpha = 0.025$:

$H_0: P_s \geq 12\%$

$H_a: P_s < 12\%$,

where P_s is the probability of a safety event in subjects from the cryoballoon arm.

15.2.2. Endpoint Definition

A primary safety event is defined as a serious procedure-related or cryoablation system-related adverse event that includes any of the following:

- TIA within 7 days
- Cerebrovascular accident within 7 days
- Major bleeding that requires transfusion or results in a 20% or greater fall in hematocrit (HCT) within 7 days
- Development of a significant pericardial effusion within 30 days. A significant pericardial effusion is one that results in hemodynamic compromise, requires elective or urgent pericardiocentesis, or results in a 1-cm or more pericardial effusion as documented by echocardiography.
- Symptomatic PV stenosis within 12 months; accompanied by one of the following: 50%-75% reduction in diameter of the pulmonary vein, with symptoms not explained by other conditions; OR >75% reduction in diameter of the pulmonary vein
- MI within 7 days
- PNI unresolved at 12 months
- AE fistula within 12 months
- Major vascular complication that requires intervention, prolongs the hospital stay, or requires hospital admission (within 7 days).

15.2.3. Performance requirements

If the upper bound of the two-sided 95% confidence interval of the safety event rate in cryoballoon arm subjects is <12%, this objective will be considered met.

15.2.4. Rationale for Performance Criteria

The safety endpoint definition and performance goal (PG) of 12% for safety events were based on previous and current Medtronic cryoballoon ablation catheter studies, as well as based on feedback from FDA staff.

A primary safety event rate of 3.1% was observed in the STOP AF trial. The 2016 Annual Report for the STOP AF PAS study reports a 12 month safety event rate of 2.3%. For this study, the safety event definition has been expanded according to FDA guidance, and certain events (e.g., symptomatic PV

stenosis from 50 – 75%, cardiac perforation/tamponade from 8 – 30 days after the procedure) not included in the two previous studies will be included. Based on the STOP AF trial and STOP AF PAS adverse event data and the expanded safety event definition, it is estimated that the current study will have a safety rate of 4.0%.

The STOP AF pivotal study and STOP AF Post-Approval Study (STOP AF PAS) both set PG requirements of 14.8%. With an estimated 4% safety rate, a PG of 12% provides stricter criteria than used in prior cryoballoon studies, in order to account for differences in the study populations.

Additionally, the STOP AF Pivotal trial reported that 8.5% of subject's experienced a Major Atrial Fibrillation Events (MAFEs) in the AAD arm (Packer et al., 2013). A large systematic review also reported that withdrawals from AADs due to adverse events averaged 16.2% for Class I AADs and 11.4% for Class III AAD's (Lafuente-Lafuente, Valembouis, et al. 2015). Therefore the performance criteria established in this study is appropriate for demonstrating an acceptable risk-benefit in this drug-naïve PAF population.

15.2.5. Analysis Methods

The probability of a safety event within 12 months will be estimated using Kaplan-Meier survival analysis. Greenwood's formula will be used to approximate the standard error of the survival curve, and a two-sided log-log confidence interval at 12 months will be reported.

Day 0 is defined as the day of the index cryoablation procedure. For subjects with a safety event, the survival date will be set to the date of the safety event. For subjects without a safety event, censoring will occur at the last study contact date with a corresponding CRF (i.e., the last study visit, exit date or death). If a subject without a safety event is lost to follow-up they will be censored on the date of the last study visit.

Any subsequent ablations a subject may have after day 0 will not reset their survival time; the date of the index procedure will remain as day 0 for purposes of the primary safety analysis. Safety events related to repeat ablation procedures occurring up to 365 days after the index cryoablation date will be considered as having met criteria for the primary safety endpoint, and will be counted as failures for this analysis.

15.2.6. Sample Size

Sample size assumptions are:

- One-sample, one-sided exact binomial test
- Alpha = 0.025
- Cryoballoon ablation 12-month safety rate = 4%
- PG = 12%
- Attrition from randomization to 1 year = 10%

Under these conditions, 210 randomized subjects are required at 1:1 randomization and 10% attrition in order to expect 94 randomized and analyzable subjects at 12-month follow-up in the cryoballoon ablation arm, which affords 80% power for a one-sided binomial test with $\alpha = 0.025$.

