15.2.7. Determination of Patients/Data for Analysis

All subjects randomized to the cryoablation arm and have the Arctic Front Advance Cardiac CryoAblation Catheter inserted into vasculature will be included.

Subjects randomized to the AAD arm who receive a cryoablation procedure during follow-up will not be included in the primary safety analysis; however, safety events occurring in these subjects will be reported into the study database and summarized.

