### 6.2.3.3. Performance Requirements

If the upper bound of the two-sided 95% confidence interval of the safety event rate in cryoablation arm subjects is <12%, this objective will be considered met.

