### 6.2.3.4. Analysis Methods

The probability of a safety event within 12 months will be estimated using Kaplan-Meier survival analysis. Greenwood's formula will be used to approximate the standard error of the survival curve, and a two-sided log-log confidence interval at 12 months will be reported.

Day 0 is defined as the day of the index cryoablation procedure. For subjects with a safety event, the survival date will be set to the date of the safety event. For subjects without a safety event, censoring will occur at the last study contact date with a corresponding CRF (i.e., the last study visit, exit date or death). If a subject without a safety event is lost to follow-up they will be censored on the date of the last study visit.

Any subsequent ablations a subject may have after day 0 will not reset their survival time; the date of the index procedure will remain as day 0 for purposes of the primary safety analysis. Safety events related to repeat ablation procedures occurring up to 365 days after the index cryoablation date will be considered as having met criteria for the primary safety endpoint, and will be counted as failures for this analysis. Safety events only observed at 12-month follow-up visits that occur 365 - 395 days after the index ablation (i.e. are in the visit window) will also count as safety failures at one year. Like with the primary efficacy objective, safety events found at 12-month visits outside of the window (>395 days from index ablation) will not be counted in this endpoint, but will be described in AE listings.

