Essentially, this process goes through the hypothetical exercise of sequentially assuming unobserved control arm subjects are successes, and unobserved treatment arm subjects are failures the day after being lost to follow-up until the log-rank test supports a different conclusion (in this case, when  $p \geq 0.05$ ). This first subject for which  $p < 0.05$  is no longer true is the point at which the analysis 'tips'. Larger numbers of treatment failures and control successes needed to change the conclusion indicate findings that are more robust to informative censoring. If the primary efficacy analysis as specified in section 6.2.2.4 shows  $p \geq 0.05$ , the tipping point analysis will be modified to quantify how many treatment arm successes and control arm failures would be necessary to reach a different conclusion for the hypothesis test.

The primary safety endpoint is only measured in the cryoablation arm. As such, the algorithm to find the tipping point of the primary safety algorithm is slightly different. Like with the efficacy tipping point analysis, data will be sorted by ascending event times, and subjects who are censored prior to 365 days are assigned an event time equal to (date of last contact - index ablation date). Then, for each observation:

- 1) If a failure is observed, skip steps 2 and 3;
- 2) If the observation is censored, set time = time + 1 and event = 1.
- 3) Apply the log-rank test specified in section 6.2.3.4 to find the new two-sided p-value and 95% log-log confidence interval.
- 4) If  $P$  is still  $< 0.05$  and a larger event time  $< 365$  exists, repeat the process with that observation; otherwise stop.

The first observation where the confidence interval includes 12.0% is the tipping point for the primary safety analysis. This analysis will be performed in the CTR dataset. For either primary endpoint, if fewer than 5 subjects have missing data, a worst-case analysis will be done instead of a tipping point analysis.

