## 7.2. Sample Size Determination for Primary Safety Objective

Sample size was estimated using Proc Power in SAS 9.4. The parameters of the calculation were for a one-sided exact binomial test with  $\alpha = 0.025$  and 80% power, with a true safety event rate of 4.0% and a performance goal of 12%. The same conditions for attrition (10% from enrollment to 12 months) and randomization ratio (1:1) were assumed in this calculation as they were for the primary efficacy endpoint. The event rate of 4% was derived by applying the definition of the primary safety endpoint retrospectively to subjects from the STOP AF pivotal study; when this was performed, event rates of 5/163 (3.1%) or 7/163 (4.3%) were observed, depending on how asymptomatic phrenic nerve injuries were counted.

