### Computed Power

[figure not shown]
Lower Crit Val	Upper Crit Val	Actual Alpha	Power
5	.	0.0246	0.825

Under the above conditions, 80% power is achieved with 94 cryoablation arm subjects analyzed. Assuming 10% attrition, then 105 enrolled subjects are needed, requiring 210 subjects to be enrolled and randomized 1:1.

The required sample size of 210 is the smallest number that results in adequate power for both the primary efficacy and safety analyses under the specified conditions, and will be used as the enrollment target for the study. Figures 2 and 3 (below) show the sensitivity of the STOP AF First power calculations to deviations from the event rate assumptions used above, for the efficacy and safety endpoints, respectively.

[figure not shown]

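### The 80% power for the primary safety objective is for an exact binomial test. Under the Kaplan-Meier log-log bound that decides it, power is 67.7% with 94 fully followed and about 76–77% with 105 treated and 10% dropout

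*Protocol*

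**What the plan says.** Sizing. Protocol 15.2.6 assumes a one-sample, one-sided exact binomial test, alpha 0.025, a true 12-month event rate of 4%, a performance goal of 12% and 10% attrition. It concludes that 210 randomized subjects should give 94 analyzable in the cryoablation arm, "which affords 80% power for a one-sided binomial test with" alpha 0.025. SAP 7.2 repeats this: "Under the above conditions, 80% power is achieved with 94 cryoablation arm subjects analyzed". Its output table shows a critical value of 5, actual alpha 0.0246 and power 0.825. It then states: "The required sample size of 210 is the smallest number that results in adequate power for both the primary efficacy and safety analyses". SAP 6.8 confirms that safety, not efficacy, drives the trial size.

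Decision. SAP 6.2.3.3 (and Protocol 15.2.3) declares the objective met on a different basis: "If the upper bound of the two-sided 95% confidence interval of the safety event rate in cryoablation arm subjects is <12" percent. Neither of those sections names the interval. The analysis sections do (Protocol 15.2.5, SAP 6.2.3.4): Kaplan-Meier estimate, Greenwood standard error, and "a two-sided log-log confidence interval at 12 months will be reported". SAP 6.4.1 recalculates the 95% log-log interval in the tipping-point analysis and compares it with the goal: "The first observation where the confidence interval includes 12.0% is the tipping point for the primary safety analysis".

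Cohort. Protocol 15.2.7: "All subjects randomized to the cryoablation arm and have the Arctic Front Advance Cardiac CryoAblation Catheter inserted into vasculature will be included". SAP 6.1.3 and 6.2.3.5 say the same, and subjects who leave early are censored, not dropped.

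**The concern.** The trial is sized for one test on one set of subjects, and decided by another rule on another set. The choice of 94 depends closely on the test: it is the first n at which the exact test allows 5 events (at 93 it allows 4). A slightly stricter interval therefore removes an allowed event and a large part of the power.

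Both documents note that their sizing test is conservative relative to the Kaplan-Meier analysis, but only for efficacy (Protocol 15.1.6, SAP 7.1). For safety at n = 94 the direction is reversed: the sizing test is the more lenient of the two.

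What is at stake is the probability that a device performing exactly as assumed misses its safety goal. Secondary testing also depends on this, because it proceeds only if the primary objectives are met.

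**Working it through.** **Inputs** (Protocol 15.2.6, SAP 7.2): true rate 0.04, goal 0.12, one-sided alpha 0.025, 94 analyzable, 105 per arm, 10% attrition.

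**Step 1. Reproduce the plan's figure.** Exact binomial, n = 94, success if X ≤ 5:
- P(X ≤ 5 | 0.12) = 0.0246
- P(X ≤ 5 | 0.04) = 0.8252

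Both match SAP 7.2. Attrition: 94/0.90 = 104.4, rounded up to 105 per arm, 210 in total.

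**Step 2. Apply the decision rule.** With complete follow-up and d events in n, put L = −ln(1 − d/n). The log-log upper limit for the event probability is

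1 − exp{ −L × exp[ 1.96 × sqrt(d/(n(n−d))) / L ] }

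For d = 5, n = 94:
- L = 0.05466
- sqrt(5/(94 × 89)) = 0.02445, and 0.02445/L = 0.4473
- exp(1.96 × 0.4473) = 2.403
- limit = 1 − exp(−0.05466 × 2.403) = 0.1231, which fails

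For d = 4, n = 94 the limit is 0.1094, which passes. The exact (Clopper-Pearson) limit for 5/94 is 0.1198, which passes. So the exact test allows 5 events and the planned rule allows 4.

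**Step 3. Power with complete follow-up, true rate 4%.**

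| n | Events allowed, exact | Power, exact | Events allowed, log-log | Power, log-log | Alpha, log-log |
|---|---|---|---|---|---|
| 94 | 5 | 82.5% | 4 | 67.7% | 0.009 |
| 96 | 5 | 81.3% | 4 | 66.1% | 0.008 |
| 97 | 5 | 80.7% | 5 | 80.7% | 0.019 |
| 98 | 5 | 80.1% | 5 | 80.1% | 0.018 |
| 99 | 5 | 79.5% | 5 | 79.5% | 0.017 |
| 105 | 5 | 75.6% | 5 | 75.6% | 0.010 |

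The interval itself costs power at n = 94–96. From 97 to 105 the two rules coincide, and the decline below 80% from n = 99 is binomial discreteness.

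**Step 4. The cohort as planned: 105 randomized to cryoablation, 10% attrition.** The documents give no timing for events or dropout, so the timings below are assumptions. The dropout rows are Kaplan-Meier simulations with 20,000 to 30,000 runs per scenario and zero events counted as success.

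| Assumption | Power |
|---|---|
| Dropout uniform over the year, 50–100% of events by day 30 | 75.6–77.3% |
| Dropout uniform, events uniform over the year | 77.4% |
| All dropout in the first 30 days | 74.3–77.7% |
| Dropout uniform, every event at 12 months | 71.1% |
| All attrition before catheter insertion | 71.3% |

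The last row is an exact calculation: treated n is binomial (105, 0.90), averaged over the log-log power at each n.

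**Step 5. Sensitivity to the event rate** (log-log rule, complete follow-up). The rates come from the documents: 2.3% from the post-approval study (Protocol 15.2.4), and the retrospective application in SAP 7.2, where "event rates of 5/163 (3.1%) or 7/163 (4.3%) were observed".

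| True rate | n = 94 | n = 105 |
|---|---|---|
| 2.3% | 93.4% | 96.5% |
| 5/163 | 83.7% | 89.5% |
| 4% | 67.7% | 75.6% |
| 7/163 | 62.2% | 70.3% |

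**Step 6. Zero events.** With d = 0, L = 0 and the log-log limit is undefined. At a 4% rate the probability of this is 0.96^94 = 2.2%, or 0.96^105 = 1.4%. No convention is given.

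**The case against.** The power figure is correctly labelled: Protocol 15.2.6 says it is for a binomial test, and the arithmetic is right. This is a mismatch between sizing and analysis methods, not a miscalculation. That is fair. It does not make the figure the power of the rule that decides the objective, which is how a reader will take it.

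The 67.7% describes 94 subjects treated and fully followed, which is not the expected cohort. At 97–105 subjects the exact test has the same power as the log-log rule, so there the loss is not due to the interval. Both points stand, and they limit the claim: the interval explains the loss only at 94–96. But neither method gives 80% at 105.

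The 76–77% rests on assumed timing. This also stands. The attrition runs from randomization, so some losses may come before catheter insertion, and phrenic nerve injury unresolved at 12 months may be dated late. The range of about 71–78% should accompany any single figure.

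Measured against the 80% target and not the computed 82.5%, the gap at 105 treated is about 3–4 points, and at 5/163 or lower the power exceeds 80%. That is true, but 4% is the plan's own assumption, and at 7/163 power is lower still.

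SAP Figure 3 (safety power by true event rate) could not be seen. The surrounding text suggests that it rests on the same exact calculation, but this was not checked.

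**Conclusion.** The concern holds. At the assumed 4% rate, the Kaplan-Meier log-log rule has 67.7% power with 94 subjects fully followed. With 105 treated it has 75.6% power if all are fully followed and about 76–77% with 10% dropout over the year; less favourable timing takes it to about 71%. The text of neither document gives power for this rule in this cohort.

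The chance that a device performing as assumed misses the goal is therefore about 23–24% (105 treated) or 32% (94 fully followed), against the 17.5% implied by the SAP's 0.825.

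The n = 94 and n = 105 results with complete follow-up need no timing assumption; the dropout results do. Reading the criterion as log-log rests on the analysis and tipping-point sections, since the criterion itself does not name the interval. Type I error stayed below 0.025 in every case checked, so a positive safety result would remain valid. The fault is an overstated chance of success, and a sample size of 210 justified by a test that is not the decision rule. It should be fixed.

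**What to change.** Keep the Kaplan-Meier rule and the treated cohort, and make three changes:

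1. In Protocol 15.2.6 and SAP 7.2, restate power for the log-log rule: about 68% with 94 fully followed and about 76% with 105 treated and 10% attrition. State the timing assumptions and show the 71–78% range. Redraw SAP Figure 3 on the same rule if it uses the exact test.
2. In Protocol 15.2.3 and SAP 6.2.3.3, name the Kaplan-Meier log-log interval with Greenwood standard error as the one compared with 12%.
3. State that with zero events the bound is the exact (Clopper-Pearson) 95% upper limit, 1 − 0.025^(1/n): 3.8% at n = 94 and 3.5% at n = 105.

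The decision should not be moved to an exact bound in completers to recover the 80%, because that would discard treated subjects with partial follow-up.

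The cost is wording in four sections and one recalculated figure. The estimator, analysis set and number of patients do not change. The stated power becomes less favourable, and these changes do not restore it to 80%.

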15.2.7. Determination of Patients/Data for Analysis

All subjects randomized to the cryoablation arm and have the Arctic Front Advance Cardiac CryoAblation Catheter inserted into vasculature will be included.

Subjects randomized to the AAD arm who receive a cryoablation procedure during follow-up will not be included in the primary safety analysis; however, safety events occurring in these subjects will be reported into the study database and summarized.

15.3. Secondary Objectives

Two secondary objectives will be evaluated to gain additional information about the performance of the Arctic Front Advance Cardiac CryoAblation catheter, with four hypotheses to be tested.

Secondary Objective #1:

Assess changes in quality of life between baseline and 12 months in the cryoballoon ablation arm. There are two hypotheses tested in the objective, with separate hypothesis tests for (1) the difference in composite scores from the AFEQT questionnaire taken at baseline and 12 month visits, and (2) for the difference in composite scores for the EQ-5D questionnaire taken at baseline and 12-month visits.

Secondary Objective #2:

Compare health care utilization between the treatment and control arms. There are two hypotheses tested in the objective, with separate hypothesis tests for: (1) the rate of total health care utilization events (cardiovascular-related hospitalizations, emergency room visits, or unscheduled office visits) over 12 months, and (2) the rate of cardioversions (electrical or pharmacological) over 12 months.

Testing for these objectives will be performed if the primary objectives are met. A Hochberg multiple testing procedure will be utilized to maintain an overall type I error rate of 0.05 for the four hypotheses being tested among the two secondary objectives.

The Hochberg procedure is a stepwise procedure and will be implemented as follows:

The four hypotheses will be defined as H(1), H(2), H(3), and H(4). For each of the hypotheses, p-values will be calculated and sorted $p(1) < p(2) < p(3) < p(4)$. The decision rule to accept or reject each hypothesis will follow the step-up algorithm, where $\alpha=0.05$:

Step 1: If $p(4) \geq \alpha$, accept H(4) and go to Step 2, otherwise reject all hypotheses and stop

Step 2: If $p(3) \geq \alpha/2$, accept H(3) and go to Step 3, otherwise reject H(3), H(2) and H(1) and stop

Step 3: if $p(2) \geq \alpha/3$, accept H(2) and go to Step 4, otherwise reject H(2) and H(1) and stop

Step 4: If $p(1) < \alpha/4$, reject H(1); otherwise accept H(1)

15.3.1. Atrial Fibrillation Effect on Quality-of-Life (AFEQT)

15.3.1.1. Hypothesis

The following hypothesis will be tested in a two-sided test:

$H_0: AFEQT_{\text{month12}} = AFEQT_{\text{baseline}}$

$H_a: AFEQT_{\text{month12}} \neq AFEQT_{\text{baseline}}$

Where $AFEQT_{\text{baseline}}$ is the score from the AFEQT assessed at the baseline visit, and $AFEQT_{\text{month12}}$ is the composite score from the AFEQT assessment from the 12-month follow-up.

15.3.1.2. Endpoint Definition

The AFEQT questionnaire will be utilized for this objective. The questionnaire is an atrial fibrillation specific health-related quality of life questionnaire to assess the impact of AF on a subject's life. The overall score ranges from 0 – 100, with 0 corresponding to complete disability and 100 corresponding to no disability. The absolute difference between each subject's baseline and 12 month scores is the endpoint of interest.

